## 2.7 Protocol Particular Disease Description

Brain malignancy will be defined as suspected or pathologically proven space-occupying intra-axial lesion. Suspected (not pathologically proven) brain malignancy will require confirmed suspicion from a neurosurgery and neuroradiology collaborator.

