## 3 ELIGIBILITY

### 3.1 Inclusion Criteria

#### Patients

- 13 years old and above.
- Written Informed consent must be obtained by the patient (age 13-17)'s parent or legally authorized representative (LAR)
- Patients must meet one set of inclusion criteria:
  - Newly identified and untreated primary brain tumor or metastasis of at least 5 mm or greater in size.
    - Suspected central nervous system neoplasms will require agreement from a study neuroradiologist and a study neurosurgeon, neuro-oncologist, or a radiation oncology that a lesion exists that is most likely either a primary brain tumor or a metastasis.
    - Patients with suspected brain metastasis must also have a history of solid organ malignancy.
  - History of primary brain tumor or metastasis treated with surgery, radiation, chemotherapy, or immunotherapy with new or increasing signal on MR imaging that is suspicious for progressive disease (treatment failure).
    - Suspected recurrent neoplasms will require agreement from a study neuroradiologist and a study neurosurgeon, radiation oncologist, or neuro-oncologist that lesion behavior is suspicious for recurrent disease.

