## 7.2 Overview

Patients with untreated disease (new lesions) will be categorized as having brain metastasis, primary brain tumor, or non-tumor based upon the following:

1. Patients with well-defined intra-axial lesions seen in the setting of pathology-proven solid organ malignancy will be considered metastasis.
2. Patients without history of a primary malignancy and agreement on a likely diagnosis of primary brain tumor by both a neurosurgical and neuroradiology co-investigator will be considered primary brain tumor.
3. Patients that do not the above criteria will be categorized as having non-tumor.

Patients in categories 1 and 2 will be further classified as having received treatment and not having received treatment.

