## 7.3 Sample Size

The healthy volunteers' data will only be used for fMRI sequence optimization, quality assurance and will not yield data for the study. The optimization scans on healthy volunteers will not affect the statistical results.

Patients will be divided into 5 groups as discussed above. It is assumed that 90% of patients enrolled will represent either brain metastasis or primary brain tumor, approximately half in each category. We also expect approximately half of each group to have received treatment. We thus expect to have approximately 20-25 patients in each of the first four groups (metastasis with and without treatment and primary brain tumor with and without treatment). The other 10% will be in group 5 and are assumed to be non-tumor mimics of malignancy (for example, stroke, demyelinating disease).

For the primary endpoints, the objective is to calculate the contrast-to-noise ratio (CNR) or equivalent parameter for each method for both primary brain tumors and metastases separately by whether the patient has received treatment. For each imaging modality, we will calculate the CNR separately in the largest lesion/metastasis per patient as well as in all study lesions (see 5.1.3). As an example, for CEST, under the assumption of only a single lesion per patient and an expected mean CEST CNR of 14.9 and corresponding standard deviation of 3.0, 20 patients in a group will give a 95% confidence interval between 13.6 and 16.2. [40] Similar calculations apply for the CNR for each of the other imaging modalities.

We may also combine groups for the purpose of analysis. Continuing the above example, with 45 patients in a group, and the same assumed mean and standard deviation, a 95% confidence interval around the CEST CNR will range from 14.0 to 15.8. Again, similar calculations apply for other imaging modalities.

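### Sections 2.7, 3.1 and 7.2 name different specialist pairs for accepting a suspected brain tumour, so a validly enrolled untreated primary tumour can default to non-tumor

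*Combined protocol and SAP*

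**What the plan says.** Three sections say whose opinion is needed for a suspected tumour.

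- **Section 3.1 (entry, untreated).** A suspected neoplasm needs "agreement from a study neuroradiologist and a study neurosurgeon, neuro-oncologist, or a radiation oncology" opinion that the lesion is most likely a primary tumour or a metastasis. A neuroradiologist plus any one of the other three is enough.
- **Section 2.7 (disease definition).** A malignancy that is suspected but not proven by pathology "will require confirmed suspicion from a neurosurgery and neuroradiology collaborator".
- **Section 7.2, rule 2 (analysis class).** For a patient with no history of a primary malignancy, "agreement on a likely diagnosis of primary brain tumor by both a neurosurgical and neuroradiology co-investigator will be considered primary brain tumor".

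Section 7.2 rule 1 assigns well-defined lesions in patients with a proven solid organ cancer to metastasis. Rule 3 is the default: "Patients that do not the above criteria will be categorized as having non-tumor".

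Section 7.3 says of that default group: "The other 10% will be in group 5 and are assumed to be non-tumor mimics of malignancy", giving stroke and demyelinating disease as examples. The primary CNR endpoint in 7.3 is calculated for primary tumours and metastases, by treatment status. Group 5 is not part of it.

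**The concern.** Entry and analysis class rest on different specialist pairs, and nothing in the plan links them. Two study specialists may have judged a lesion most likely a tumour, exactly as 3.1 asks. It can still be labelled non-tumor only because neither of the two opinions came from neurosurgery.

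The untreated primary-tumour group in objective 1.1.1 is at stake. Whether a patient counts in it should depend on what the lesion is judged to be, and rule 3 makes it depend also on which specialty gave the opinion. The group may then be smaller than planned, and group 5 may hold lesions that 7.3 does not describe.

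**Working it through.** **Step 1: follow one patient through the rules.** Take an untreated patient with a suspected primary tumour and no cancer history, enrolled on a neuroradiologist's and a neuro-oncologist's agreement.

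- Section 3.1: met.
- Section 7.2 rule 1: not met, because there is no solid organ malignancy.
- Section 7.2 rule 2: not met unless a neurosurgical co-investigator also agrees.
- Section 7.2 rule 3: non-tumor by default, and so outside the primary CNR estimate.

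**Step 2: look for a step that closes the gap.** Section 4.1 goes from confirmed eligibility to consent and enrolment. Section 4.7 lets participation end when the scan is done. Section 7.2 gives no time for its agreement. No section requires a neurosurgical review of every patient before classification, or lets another specialist stand in under rule 2. Section 2.7 would close the gap for suspected lesions if applied at entry, but 3.1 does not ask for it.

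**Step 3: reproduce the plan's figures (section 7.3).** Inputs: CEST CNR mean 14.9, SD 3.0, 100 patients, 90% tumours, half primary, half of each treated.

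- n = 20: half-width = 1.96 × 3.0/√20 = 1.31, giving 13.6 to 16.2, as stated.
- n = 45: half-width = 1.96 × 3.0/√45 = 0.88, giving 14.0 to 15.8, as stated.
- Expected untreated primary tumours: 100 × 0.9 × 0.5 × 0.5 = 22.5, within the stated 20 to 25.

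**Step 4: size of the loss.** Let f be the share of untreated primary tumours that never receive a neurosurgical co-investigator's agreement. The documents do not give f, so the range below is an assumption and starts at zero. Patients left: n = 22.5(1 − f). Half-width: 1.96 × 3.0/√n. The comparison is with the plan's n = 20, so the ratio is √(20/n). Group 5 becomes 10 + 22.5f, of which 22.5f are likely tumours.

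| f | moved | n left | half-width | ratio to n = 20 | group 5 | likely tumours in group 5 |
|---|---|---|---|---|---|---|
| 0% | 0 | 22.5 | 1.24 | 0.94 | 10 | 0% |
| 10% | 2.25 | 20.25 | 1.31 | 0.99 | 12.25 | 18% |
| 20% | 4.5 | 18 | 1.39 | 1.05 | 14.5 | 31% |
| 1/3 | 7.5 | 15 | 1.52 | 1.15 | 17.5 | 43% |
| 50% | 11.25 | 11.25 | 1.75 | 1.33 | 21.25 | 53% |

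The group falls below 20 when 22.5(1 − f) < 20, that is f > 1 − 20/22.5 = 11%.

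**Step 5: scope.** The rules in 7.2 open with "Patients with untreated disease (new lesions) will be categorized as having brain metastasis, primary brain tumor, or non-tumor based upon the following", so the direct effect is on the untreated primary group. The section then adds that "Patients in categories 1 and 2 will be further classified as having received treatment and not having received treatment", which leaves the classing of treated patients unclear. Entry for suspected recurrence uses the wider panel too ("agreement from a study neuroradiologist and a study neurosurgeon, radiation oncologist, or neuro-oncologist that lesion behavior is suspicious for recurrent disease"), so if rule 2 is also applied to treated patients the same gap opens there. That possibility is not counted above.

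**The case against.** The strongest reply is that 3.1 and 7.2 do different jobs. Section 3.1 is an entry gate that asks whether the lesion is most likely a tumour of either kind. Section 7.2 asks whether primary tumour is the likely diagnosis, and sets no deadline. A neurosurgical co-investigator could agree at any time before analysis. The figures in 7.3 fit that view: 3.1 admits suspected untreated lesions only when tumour is thought most likely, yet 7.3 expects 10% mimics, which suggests a later and separate judgement. Section 2.7, if enforced, would also give every suspected lesion a neurosurgical opinion and bring f close to zero.

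Most of this stands. A reader might infer that every patient admitted without a neurosurgeon is lost, and the documents do not support that. A patient is lost only if neurosurgical agreement never comes. What remains is that the plan does not require that agreement for every patient, and that 2.7, if enforced, contradicts 3.1.

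A reader might also infer that the loss is selective, for example that the group is tilted towards operable lesions. The documents describe no referral routes and no link between resectability and CNR, so there is no support for a direction of bias. Nor does likely tumour in group 5 distort a planned result, since sections 7.3 and 7.4 specify no estimate or comparison for that group.

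**Conclusion.** The inconsistency is real and stands in the current text. Read as written, rules 2 and 3 can put a validly enrolled untreated primary tumour in the wrong class and take it out of a primary estimate. How often this would happen is unknown, and it may be never.

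The loss of precision is small at low shares. Up to f of about 11% the group still holds the 20 patients behind the plan's interval. At f = 20% the half-width is about 5% larger than planned (1.39 against 1.31), and at f = 50% about a third larger (1.75). These figures assume 22.5 expected patients, an SD of 3.0 that does not change with f, and one lesion per patient. The plan's own intervals are reproduced and are not in dispute. The primary objective is estimation with no test, so no power is lost. The reason to act is that class membership should follow the judgement on the lesion, and the repair is cheap.

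**What to change.** - In 7.2 rule 2, replace the required neurosurgical and neuroradiology pair with the 3.1 panel: a study neuroradiologist plus a study neurosurgeon, neuro-oncologist or radiation oncologist. Make 2.7 match.
- Keep classification as its own recorded judgement of primary tumour, metastasis or non-tumour, and state when and by whom it is made. It should also cover pathologically proven lesions, because rule 2 has no pathology route and the 3.1 agreement is written for suspected lesions only.
- Leave rule 1 unchanged.
- Reserve category 3 for lesions judged not to be tumour, as 7.3 describes, and not for cases that lack one specialty's agreement.

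The entry agreement should not itself fill categories 1 and 2. Almost no suspected case could then reach category 3, rule 1's cancer-history criterion would be overridden, and proven tumours would be missed.

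The cost is wording in 2.7 and 7.2 and a recorded classification for each patient, with no added scan. The small downside is that category 2 would not always carry a neurosurgeon's opinion.

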## 7.3 Sample Size

The healthy volunteers' data will only be used for fMRI sequence optimization, quality assurance and will not yield data for the study. The optimization scans on healthy volunteers will not affect the statistical results.

Patients will be divided into 5 groups as discussed above. It is assumed that 90% of patients enrolled will represent either brain metastasis or primary brain tumor, approximately half in each category. We also expect approximately half of each group to have received treatment. We thus expect to have approximately 20-25 patients in each of the first four groups (metastasis with and without treatment and primary brain tumor with and without treatment). The other 10% will be in group 5 and are assumed to be non-tumor mimics of malignancy (for example, stroke, demyelinating disease).

For the primary endpoints, the objective is to calculate the contrast-to-noise ratio (CNR) or equivalent parameter for each method for both primary brain tumors and metastases separately by whether the patient has received treatment. For each imaging modality, we will calculate the CNR separately in the largest lesion/metastasis per patient as well as in all study lesions (see 5.1.3). As an example, for CEST, under the assumption of only a single lesion per patient and an expected mean CEST CNR of 14.9 and corresponding standard deviation of 3.0, 20 patients in a group will give a 95% confidence interval between 13.6 and 16.2. [40] Similar calculations apply for the CNR for each of the other imaging modalities.

We may also combine groups for the purpose of analysis. Continuing the above example, with 45 patients in a group, and the same assumed mean and standard deviation, a 95% confidence interval around the CEST CNR will range from 14.0 to 15.8. Again, similar calculations apply for other imaging modalities.

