## 3.3 NUMBER OF PARTICIPANTS

One hundred (100) patients will be studied. Up to twenty (20) healthy volunteers will be studied for the purposes of MRI sequence optimization.

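### The precision quoted for 20 patients per group treats the SD as known and is slightly optimistic, and 20 should not be read as a minimum group size

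*Combined protocol and SAP*

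**What the plan says.** The primary objective (section 1.1) is to estimate the contrast-to-noise ratio (CNR) of each imaging method separately by type of malignancy and treatment status. That gives four groups.

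Section 3.3 sets the total: "One hundred (100) patients will be studied". Section 7.3 then builds the group sizes from three expectations. The first is stated as "It is assumed that 90% of patients enrolled will represent either brain metastasis or primary brain tumor, approximately half in each category". The second is that treated and untreated patients will be split about evenly within each tumour type. The third is that "The other 10% will be in group 5". From these the section concludes "We thus expect to have approximately 20-25 patients in each of the first four groups".

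Precision is shown by a worked example for CEST, with one lesion per patient and "an expected mean CEST CNR of 14.9 and corresponding standard deviation of 3.0". On that basis "20 patients in a group will give a 95% confidence interval between 13.6 and 16.2". A second example, for combined groups of 45, gives 14.0 to 15.8. The other modalities are said to follow similar calculations.

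Section 7.4 says that each CNR will be reported with its 95% confidence interval but does not name the method. Neither the eligibility and enrolment sections nor section 7 sets a quota, cap or minimum per group.

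**The concern.** In an estimation study the projected interval width is the design claim. The 20-patient example is the only precision figure given for the four separate primary groups, so it should describe what 20 patients would deliver.

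Two features make it look better than that. First, the figure matches a calculation with a known SD, whereas each group's SD will have to be estimated from its own patients. Second, 20 is the lower end of the expected range, so the example can be taken for a conservative case. The range surrounds an average of 22.5, however, and nothing in the plan holds each group at 20 or more. At stake is a modest overstatement of precision for the smallest groups. No test or success criterion is affected.

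**Working it through.** **Inputs.** Mean 14.9, SD 3.0, n = 20 and n = 45 (section 7.3); 100 patients (section 3.3); 90% tumour, about half of each type, about half of each type treated (section 7.3). Expected size per group: 100 × 0.90 × 0.5 × 0.5 = 22.5.

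**1. Reproducing the plan's figures (SD known).** The formula is mean ± 1.96 × SD/√n.
- n = 20: 3.0/√20 = 0.671; 1.96 × 0.671 = 1.315; 14.9 ± 1.315 = 13.59 to 16.21, which rounds to the stated 13.6 to 16.2.
- n = 45: half-width 0.877; 14.02 to 15.78, which rounds to the stated 14.0 to 15.8.

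Both stated intervals are reproduced.

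**2. SD estimated from the group.** The formula is mean ± t(0.975, n − 1) × SD/√n, evaluated at the assumed SD of 3.0.

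| n | t quantile | half-width | interval |
|---|---|---|---|
| 15 | 2.145 | 1.66 | 13.2 to 16.6 |
| 18 | 2.110 | 1.49 | 13.4 to 16.4 |
| 20 | 2.093 | 1.40 | 13.5 to 16.3 |
| 22 | 2.080 | 1.33 | 13.6 to 16.2 |
| 23 | 2.074 | 1.30 | 13.6 to 16.2 |
| 25 | 2.064 | 1.24 | 13.7 to 16.1 |
| 45 | 2.015 | 0.90 | 14.0 to 15.8 |

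At n = 20 the ratio of half-widths is 1.404/1.315 = 1.068, and the difference is 0.09 per side. The stated figures first appear, after rounding, at n = 22 (13.57 to 16.23). At n = 45 the two methods agree to the precision shown.

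**3. Group sizes.** Added assumption: each patient falls independently into one of the four tumour groups with probability 0.225 each, or into the non-tumour group with probability 0.10, with no quota.
- One given group: SD of its size = √(100 × 0.225 × 0.775) = 4.18; P(fewer than 20) = 0.24.
- Four groups, exact multinomial: P(all four at least 20) = 0.23, so P(at least one below 20) = 0.77. The smallest group has median 18 and 5th to 95th percentile 14 to 21.

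Sensitivity to the allocation assumption:
- Exactly 90 tumour patients, 0.25 per group: P(at least one below 20) = 0.78.
- Exactly 45 metastasis and 45 primary, treatment split binomial with probability 0.5: within a type, both groups reach 20 when the treated count is 20 to 25, with probability 0.629. Then P(at least one below 20) = 1 − 0.629² = 0.60, and the median smallest group is 19.

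**The case against.** The strongest reply is that nothing has been miscalculated. The normal quantile is a common planning approximation, the figure is offered as an example from assumed inputs, and it reproduces exactly. The shift is 0.09 CNR units per side, and no threshold, test or target width depends on it. At the expected group size of 22 to 23 the t interval rounds to the stated figures, so choosing 20 roughly offsets choosing the normal quantile. Uncertainty in the SD matters more: with an SD of 3.5 (an illustration, not a figure from the plan) the t half-width at n = 20 would be 1.64. All of this stands, and it is why the point is minor. It does not change the fact that the interval is attributed to 20 patients.

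On group size, the plan speaks only of an expectation, "approximately 20-25 patients in each of the first four groups", and promises no floor. The 0.77 rests on an allocation model that the plan does not state, and it concerns the worst of four groups; a given group has a 24% chance of falling below 20. A smallest group of 15 is a tail case. These points also stand, although the probability stays above one half under each variant tried.

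A reader might infer that the reported intervals will undercover. A normal-quantile interval with an SD estimated from 20 patients would cover about 93.5% under normality. The documents do not support that inference, because section 7.4 does not say which method the analysis will use. Nor do they support calling the stated figure an arithmetic error, or saying that the design misses its stated precision at the average group size.

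**Conclusion.** The point holds as a minor one. The interval given for 20 patients is correct for a known SD and slightly too narrow for an estimated one: 13.5 to 16.3 instead of 13.6 to 16.2, a half-width of 1.40 against 1.31. The 45-patient interval is sound.

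Twenty is an illustrative group size and not a lower bound. Under independent allocation at the plan's proportions, at least one of the four groups is more likely than not to fall below it (0.77; range 0.60 to 0.78 across the variants), with a smallest group of typically 18 or 19. At 18 the half-width is 1.49, which is 0.18 more per side than stated.

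These results take the mean of 14.9 and SD of 3.0 as given, assume roughly normal CNR values with one lesion per patient, and make no allowance for unusable scans, for which the plan gives no figure.

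**What to change.** In section 7.3:
- Restate the 20-patient interval as 13.5 to 16.3, and label it illustrative and not a minimum.
- Add t-based intervals over a plausible range of group sizes, for example n = 15: 13.2 to 16.6; n = 18: 13.4 to 16.4; n = 22: 13.6 to 16.2.
- Leave the 45-patient interval as it is.

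In section 7.4, state that the reported CNR intervals use the t distribution.

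The cost is a few lines of text, with no extra patients and no change in conduct. The downside is that the stated precision becomes slightly less favourable. The change describes the likely spread of group sizes but does not prevent a small group; only a minimum per group would do that, and this point does not depend on setting one.

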## 7.4 Analysis Plan

Patients with metastasis are expected to have on average 2-3 detectable brain lesions each. Patients with primary brain tumors are expected to have a single lesion. All analyses will be performed on the largest lesion within patients, and some analyses will be repeated on a per-lesion basis.

The CNR for each imaging method will be determined and reported along with the corresponding 95% confidence interval. In secondary analyses, for the conspicuity endpoints, the T1 sequence by MRI will be considered the gold standard, and we will compare the conspicuity of each of the other methods to that of T1 sequencing by using McNemar's test. This analysis will first be performed in the largest lesion per patient, and then analyses will be repeated using all lesions.

If enough follow-up images are obtained (see section 4.5), we will compare the CNR in lesions that respond to treatment to those that do not by using a Wilcoxon rank-sum test. We will compare the CNR between baseline and follow-up within patient by using a Wilcoxon signed-rank test. Also, for those lesions that initially respond, some will subsequently grow in size after the initial response. Of these, some will be considered radiation necrosis and some progressive disease. The CNR will be compared between lesions with necrosis and those that are progressive disease using a Wilcoxon rank-sum test.

Exploratory aims will be analyzed with descriptive statistics. fMRI paradigms will be summarized by the group mean and standard deviation. Patient satisfaction will be reported on a five-point Likert scale and compared between the 7T scan and the most recent clinical scan by using a Wilcoxon rank-sum test.

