## **5 Image Analysis**

### **5.1 Lesion size evaluation:**

- 5.1.1 A patient must have a single intraaxial brain lesion of 5 mm or greater for study inclusion as measured on either T2-weighted or T1-post contrast weighted imaging.
- 5.1.2 Lesions will be measured on either axial T2 FLAIR weighted or T1 post-contrast imaging on a slice displaying the maximal lesion size using the longest diameter after appropriate magnification on the picture archiving and communicating system (PACS) monitors.
- 5.1.3 For patients with multiple lesions appropriate for study assessment, the five (5) largest lesions will be assessed.

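### In treated patients with several lesions, the follow-up comparisons can miss the lesion that qualified the patient, because the analysed lesion is chosen by size alone

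*Combined protocol and SAP*

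**What the plan says.** **Entry.** Section 3.1 admits previously treated patients "with new or increasing signal on MR imaging that is suspicious for progressive disease (treatment failure". For suspected recurrence, a study neuroradiologist and a second specialist must agree "that lesion behavior is suspicious for recurrent disease". Size rank among the patient's lesions plays no part.

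**Lesion analysed.** Section 7.4 states: "All analyses will be performed on the largest lesion within patients". The same sentence goes on to promise lesion-level repeats of some of them, without saying which. For the primary endpoint, section 7.3 says "we will calculate the CNR separately in the largest lesion/metastasis per patient as well as in all study lesions (see 5.1.3". Section 5.1.3 sets the cap: "For patients with multiple lesions appropriate for study assessment, the five (5) largest lesions will be assessed". It does not define which lesions are appropriate.

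**Lesion counts.** Section 7.4: "Patients with metastasis are expected to have on average 2-3 detectable brain lesions each". Primary brain tumours are expected to be single.

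**Comparisons.** Section 7.4 repeats the conspicuity analysis in all lesions. It names no such repeat for the two rank-sum tests of CNR that depend on follow-up: responders against non-responders, and necrosis against progression. It introduces the second test with lesions that first respond and later grow.

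**Labels.** Under 7.1.2, recurrence is settled by pathology where available, otherwise by follow-up imaging. The imaging route requires that the lesion was first a responder (7.1.2.1) and then grew by stated amounts (7.1.2.2). Lesions that do not qualify are classed as radiation necrosis (7.1.2.3).

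**The concern.** Eligibility follows a lesion's behaviour and analysis follows its size, and no section connects the two. In a patient with several metastases, the largest may be an old treated lesion that is no longer changing, while the one that prompted enrolment is smaller or new.

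Whether a lesion is necrosis or progression is a live question only for the suspicious lesion. If the largest-lesion rule passes over it, the patient contributes either nothing or the wrong lesion to the comparison that bears most directly on objective 1.2.1. The responder comparison has the same weakness. These comparisons will draw on small numbers, so a few substituted or lost lesions matter.

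**Working it through.** **1. The plan's own figures.** Inputs from 3.3 and 7.3: 100 patients, 90% with tumour, half of those metastasis, half of each group treated; CEST CNR mean 14.9, SD 3.0.

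- Treated metastasis group: 100 × 0.90 × 0.5 × 0.5 = 22.5, within the stated 20-25.
- n = 20: 14.9 ± 1.96 × 3.0/√20 = 14.9 ± 1.31, or 13.59 to 16.21 (stated 13.6 to 16.2).
- n = 45: 14.9 ± 1.96 × 3.0/√45 = 14.9 ± 0.88, or 14.02 to 15.78 (stated 14.0 to 15.8).

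The figures reproduce. The point concerns which lesion is measured, not the arithmetic.

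**2. One patient traced through the text.** Take a treated patient with three metastases: the largest is stable and a smaller one is growing, which is why the patient was enrolled.

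| Analysis | Lesion used | Is the suspicious lesion included? |
|---|---|---|
| CNR, largest lesion (7.3) | stable one | no |
| CNR, all study lesions (7.3, 5.1.3) | all three | yes |
| Conspicuity, largest then all (7.4) | both ways | yes, in the repeat |
| Responder comparison (7.4) | stable one | no repeat named |
| Necrosis versus progression (7.4) | stable one, if any | no repeat named |

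In the last row, 7.4 confines the comparison to lesions that responded and then grew. On that text the stable lesion drops out and nothing replaces it. Under 7.1.2.3 the same lesion, without pathology, fails the recurrence criteria and is called radiation necrosis. The two passages give different answers.

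**3. How often.** The documents give no figure, so this is an assumption. Suppose one of k lesions is suspicious and the largest is w times as likely as any other single lesion to be that one. Then P(suspicious lesion is not the largest) = (k − 1)/(w + k − 1).

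| w | k = 2 | k = 3 |
|---|---|---|
| 1 (size unrelated to suspicion) | 1/2 = 50%, 11.2 of 22.5 | 2/3 = 67%, 15.0 of 22.5 |
| 2 | 1/3 = 33%, 7.5 | 2/4 = 50%, 11.2 |
| 4 | 1/5 = 20%, 4.5 | 2/6 = 33%, 7.5 |

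These counts treat every patient as having exactly k lesions, whereas 2-3 is an average. Patients with one lesion cannot be mismatched. With w = 1:

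- Half with one lesion and half with three (mean 2): 0.5 × 0 + 0.5 × 0.667 = 33%, about 7.5 patients.
- Half with one and half with four (mean 2.5): 0.5 × 0 + 0.5 × 0.75 = 37.5%, about 8.4 patients.

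Several suspicious lesions in one patient would lower the share further.

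**4. The five-lesion cap.** With five or fewer assessable lesions, the suspicious one is always inside the cap. Beyond that, with w = 1, it falls outside with probability (k − 5)/k: 1/6 = 17% for six lesions and 3/8 = 37.5% for eight.

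**The case against.** Several points on the other side are sound.

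- **A reader might infer that the suspicious lesion never reaches the main CNR analysis.** The documents do not support that. Section 7.3 calculates CNR in all study lesions beside the largest, and at two or three lesions the suspicious one is inside the cap. Objective 1.1.1 asks for CNR by tumour type and treatment status, not in suspicious lesions alone. Largest-lesion selection is objective and defensible there. What remains is that an all-lesion mean mixes suspicious and stable lesions.
- **A reader might infer that stable lesions will contaminate the necrosis group.** That follows from 7.1.2.3 read alone. The restriction in 7.4 points to loss of the patient from the comparison instead. The text supports a conflict between the passages, not one settled outcome.
- **A reader might take 50% to 67% as the expected rate.** It is the upper end of an illustration that assumes no link between size and suspicion and identical lesion counts.
- **Section 5.1.3 might already limit assessment to qualifying lesions.** Its undefined term allows that reading, but nothing states it.
- **An index-lesion rule alone could worsen labelling.** A new lesion that never responded cannot meet 7.1.2.1, so without pathology it is called necrosis. This stands, and the fix must deal with it.
- **The follow-up comparisons are conditional on enough follow-up imaging.** True, but if they are run the lesion must still be specified.

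**Conclusion.** The point holds for the responder and necrosis-versus-progression comparisons in treated patients with more than one lesion. In practice that means the treated metastasis group, about 22 of 100 patients; single-lesion primary tumours are unaffected. Among treated patients with two or three lesions, illustrative assumptions put the mismatch at about 20% to 67%. It is lower across the whole group if many patients have one lesion. These values rest on an assumed link between size and suspicion and on one suspicious lesion per patient, neither of which the documents give.

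For the primary CNR the effect is smaller: the planned largest-lesion estimate may describe a non-suspicious lesion, but the all-lesion estimate beside it includes the suspicious one unless the patient has more than five lesions. The stated confidence intervals are correct as computed.

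**What to change.** 1. **Section 7.4.** For the responder and necrosis-versus-progression comparisons in treated patients, define the index lesion as the one that met the suspicion criterion in 3.1 or, if several did, the largest of these. Keep the largest-lesion version of both comparisons as a sensitivity analysis.
2. **Enrolment and 5.1.3.** Flag the index lesion when the specialists record their agreement, before any CNR is seen, and always include it among the five lesions assessed.
3. **Section 7.3.** Keep the largest-lesion and all-lesion CNR for the primary endpoint. For the treated groups, report the index-lesion CNR alongside them.
4. **Sections 7.1.2 and 7.4.** Reconcile 7.1.2.1 and 7.1.2.3 with 7.4, so that an index lesion that is new or never responded is not classed as necrosis by default.

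**Cost.** Items 1 to 3 need one flag per lesion and a few sentences. The index-lesion analyses still use one lesion per patient, so n and the planned precision do not change if the assumed SD of 3.0 also holds for index lesions. That may not be so: index lesions may be smaller, with noisier ROIs. Item 4 takes more work, because it changes outcome definitions, but without it the index rule would bring more lesions into the default necrosis label.
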